## 2. Radiographic examination

- Standardized periapical radiographs serving as routine clinical assessment.
- Panoramic radiographs
  - Prior to implant surgery
  - Immediately after implant surgery as postoperative control
  - Immediately after second implant exposure surgery for postoperative control

## 3. Scan analysis

To be able to determine the change of bone quantity around loaded and non-loaded implants two different scans of the area with an intraoral scanner will be made.

The first scan immediately after the implant insertion and the second one four months after the insertion. As a reference scan-bodies applied to the implants will be used.

The scan-procedure will be performed according to the recommended protocol of Sirona Cerec

The two stl-data sets will be imported into the SIMPLANT (Dentsply Implants) software and matched with the optical scan modul.

The measurements between the reference points and the marginal implant bone next to unloaded or loaded implants will be documented.

## 11. Study Schedule

| Study Period                          | Screening   |    | Treatment Period |              |                 |              |             | Follow-up    |                |                |  |
|---------------------------------------|-------------|----|------------------|--------------|-----------------|--------------|-------------|--------------|----------------|----------------|--|
| Visit                                 | 1           | 2  | 3                | 4            | 5-7             | 8            | 9           | 10           | 11             | 12             |  |
| Timeline                              | -7d
+-2d | 0d | +Max 72
h     | +7d
+- 3d | +1,2,3m
+-7d | +4m
+- 7d | +4m
+-7d | +6m
+-10d | +12m
+- 10d | +24m
+- 10d |  |
| Informed consent                      |             |    |                  |              |                 |              |             |              |                |                |  |
| Health questionnaire, medical history | X           |    |                  |              |                 |              |             |              |                |                |  |
| Inclusion, exclusion criteria,        |             |    |                  |              |                 |              |             |              |                |                |  |
| Pregnancy test                        | X           |    |                  |              |                 | X            |             |              | X              | X              |  |
| OHIP-G 14                             | X           |    |                  | X            | X               |              | X           |              | X              | X              |  |
| Implant surgery and first scan        |             | X  |                  |              |                 |              |             |              |                |                |  |
| Suture removal                        |             |    |                  | X            |                 |              | X           |              |                |                |  |
| Implant exposure and second scan      |             |    |                  |              |                 |              | X           |              |                |                |  |
| Photographs                           | X           | X  | x                | X            |                 |              | X           | X            |                |                |  |
| Digital Volume Tomography             |             | x  |                  |              |                 |              |             |              |                |                |  |
| Panoramic x-ray                       | X           | X  |                  |              |                 |              | X           |              |                |                |  |

|  |  |   |   |   |   |   |   |   |   |   |
|--|--|---|---|---|---|---|---|---|---|---|
| Single tooth x-ray, probing                                |  | X |   |   |   | X |   |   | x | x |
| Clinical evaluation  |  |   | X | X | X | X | X | X | X | X |
| Conventional Impressions                                   |  | X |   |   |   | X |   |   |   |   |
| Periotest / ISQ-measurement                                |  | X |   |   | X | X |   | X | X | X |
| Implant exposure 32, 42                                    |  | X |   |   |   |   |   |   |   |   |
| Implant exposure 33, 43                                    |  | X |   |   |   |   |   |   |   |   |
| Implant exposure 34, 44                                    |  |   |   |   |   | X |   |   |   |   |
| Integration of dolder bars to implants on positions 33, 43 |  |   | X |   |   |   |   |   |   |   |
| Further Treatment for definitive prosthetic therapy        |  |   |   |   |   |   | X | X | X | X |

The use of three different implant healing protocols, the OHIP-G 14 questionnaire, the pregnancy testing and the intraoral camera scans are study-specific procedures while all other procedures are routine examinations.

## 11.1. Regulations for monitoring

The Principle Investigator consents to data evaluation being performed by the person in charge of monitoring in accordance with the monitoring plan, in order to ensure satisfactory data collection and adherence to the study protocol.

Furthermore, the Principle Investigator states that he/she is willing to cooperate with this person and shall provide this person with all required information whenever necessary. This includes access to all documents related to the trial, including study-relevant medical files of patients in original form. The tasks of the investigator include maintenance of these patients' medical files as comprehensively as possible; this includes information concerning medical history, accompanying diseases, inclusion in the trial, data about visits, results of investigations, dispensing of medication, and adverse events. The monitor will also be permitted to perform data evaluation and draw comparisons with the relevant medical files in accordance with the SOPs and ICH-GCP guidelines at predetermined intervals, in order to ensure adherence to the study protocol and continuous registration of data. All original medical reports required as sources for the information given in the CRF or the database shall be inspected. The study participants will have given their consent to such inspection by signing the consent form. The person in charge of monitoring is obliged to treat all information as confidential and to preserve the basic claims of the study participants in respect of integrity and protection of their privacy.

## 11.2. Statistical considerations

Primary and secondary variables will be evaluated descriptive and explorative.

The difference in bone loss over 4 months will be calculated for the three treatment groups.

A linear mixed model will be applied to evaluate the influence of the treatment on the bone level after 4 months. Since there are 6 implants from one patient, the patients will be included as a random effect. Treatment group will be a fixed effect.

Based on our former study we performed a sample size estimation. A sample size of 8 in each group will have 80% power to detect a difference in means of -0,580 (the difference between a Group 1 mean,  $\mu_1$  of -0.910 and a Group 2 mean,  $\mu_2$  of -0.330) assuming that the common standard deviation is 0.380 using a two group t-test with a 0.05 two-sided significance level. When the sample size in each of the 3 groups is 9, a one-way analysis of variance will have 80% power to detect at the 0.05 level a difference in means characterized by a Variance of means of 0.060, assuming that the common standard deviation is 0,380.

Based on these statistical calculations and considerations a patient sample size of 20 was determined. All statistical calculations will be performed in a significance level of 5%. Possible Drop- outs will be replaced to reach the necessary number. There will be no interim analysis.

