## 4. Synopsis

|   |   |
|---|---|
| Sponsor  | Univ.-[name].med.univ. [name]   |
| Name   | Within patient comparison of immediately loaded versus non-loaded submerged and transgingival healed implants in the edentulous mandible  |
| Running head                                       | Comparison of loaded and non-loaded implants  |
| Target population (or indication)                  | Age 20-80
Men and women
Edentulous Mandible   |
| Study design                                       | Controlled Clinical Trial   |
| Aims of the clinical trial                         | 
Primary aim of the trial
 
Marginal bone loss in different implant healing protocols over the first 4 months
 
Secondary aims of the trial
 
Implant survival rate
Measurements of Periotest / ISQ values
Biologic and prosthetic complications
Patients satisfaction
 |
| Outcome measures (endpoints) of the clinical trial | 
Primary outcome measure
 
periimplant bone level change in mm
 
Secondary outcome measures
 
Implant survival rate
Measurements of Periotest / ISQ values
Biologic and prosthetic complications
Patients satisfaction
   |
| Number of patients                                 | 20   |
| Time schedule                                      | 
With reference to the trial
 
Recruitment period: December 2016
Planned start (FPFV):February 2017
Planned end (LPLV):December 2018
 
With reference to patients
 
Duration of treatment: 4 months
  |
| Inclusion criteria                                 | 
 
• Written consent of the participant after being informed
 
  |

|                           |   |
|---------------------------|---|

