Each of these patients obtained 6 implants in the interforaminal region of the lower jaw located at positions 34, 33, 32, 42, 43, 44. The upper edges of these implants were placed at the bone level and the necessary primary stabilities of 45 Ncm were achieved. The bone level in relation to the implant margin was measured with a 1-mm gauge periodontal probe and estimated to the nearest 0.5mm. Four of the six implants were covered with cover screws.

To obtain a within patient comparison of immediately loaded and non-loaded implants, the ones at position 33 and 43 were chosen to be immediately loaded by a Dolder-bar retained overdenture. These implants were connected with a transfer coping and impressions were made with polyether. Within a period of 2-4 days of manufacturing, a Dolder-bar was integrated on these two implants.

After a delayed healing period of 6 months, second stage surgery was carried out. At this time, a full thickness flap was raised, exposing the margin of all involved implants in order to collect as much information as possible about clinical differences between loaded and non-loaded implants. The clinical parameters to be evaluated at this point were: survival rate, measurement of Periotest values (PTV, (Schulte & Lukas 1993) after mounting the gingiva formers, and assessment of marginal bone level related to the bone level at first stage surgery for loaded and non-loaded implants. Periodontal probes of 1-mm calibration were utilized for the assessment of the distance between the coronal bone level and the upper edge of the implant.

Six months post-op, the median of bone level changes was 1mm reduction of periimplant bone height for the loaded implants and 0.5mm reduction for the non-loaded implants. The corresponding mean values were 0.9mm ( $\pm 0.40$ ) and 0.33mm ( $\pm 0.34$ ), respectively. The control of significance level was achieved the same way as for the Periotest values. With  $P < 0.001$ , this difference was highly significant (Lorenzoni et al. 2003).

In our present study we want to confirm the outcomes of the former study by acquiring more precise data about the marginal bone remodelling using surface scans. In addition the bone remodelling differences between submerged and transgingival healed implants should be analysed.

Based on the results of the present pilot study, we intend to conduct a subsequent trial with two groups (immediately loaded vs. delayed loaded implants).

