rate and measurements of implant stability values after mounting the gingiva formers. Additionally a second bone-surface scan will be performed using CEREC Omnicam (Dentsply Sirona). Scan-bodies will be used to acquire a fixed reference and comparable data.

Both scans will be analysed using the Simplant-Software (Dentsply Implants). The bone contours of the surface scan images will be superimposed to measure the differences in three-dimensional space.

Clinical trials show evidently, that the bone loss measured by radiographs and by probing shows the highest bone resorption within the first three months after the insertion of dental implants. After three months a steady state, where no bone gain or loss can be measured, has been reached (Hermann et al. 2001; Brägger et al. 1998; Günther 2005; Siddiqui et al. 2001)

After contact with the implant the bone cells spread along the metal surface. This phase known as the Osteoconductive Phase continues over the first 3 months. At the time of 3-4 months after initial placement, the maximum surface area is covered by bone. The final Osteoadaptive Phase begins approximately 4 months after implant placement. It is associated with a steady state resorption remodeling sequence that continues after the implants are exposed and loaded (Arun K. Garg 2010).

GCP Statement: This study will be conducted in compliance with the principles of the Declaration of Helsinki, the ICH-GCP guidelines and in accordance with the relevant provisions of Austrian Medical Devices Act (MPG), the European Directive on implantable medical devices (90/385/EEC), the Styrian Hospitals Act (KALG), the Federal Law on hospitals (KAKuG), the EN-ISO standards 14155-1 and -2, EN ISO 14971, 10993 and all other ENISO eligible relevant legislations.

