### **Randomization and Blinding**

Due to the prosthetic restoration and in order to prevent any acting forces on the neighboring implants it is not possible to perform randomization or blinding of neither the patients nor outcome assessors. The implants are always placed at the same position and the positions of the immediately loaded and non-loaded submerged and transgingival healed implants are predetermined.

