### **Visit 2: Implant Surgery and first scan**

At visit 2 a preoperative digital volume tomography will be performed.

All surgical procedures will be performed on an outpatient basis under local anesthesia under standard conditions in septic surgery. All patients will be advised to rinse for at least 1 minute with 0.2% chlorhexidine digluconate. Preoperatively, the surgical site will be evaluated. After preparation of a full thickness flap the bone will be assessed for quality and quantity.

All patients will receive CE-certified implants of the same company and with the same design used in the Department of Oral Surgery & Radiology and Division of Prosthodontics, Restorative Dentistry, Periodontology and Implantology, Dental

School at Medical University of Graz as standard implants, that are approved in Austria (ASTRA TECH® Implant System, Dentsply Implants).

The implants will be placed in the interforaminal region at positions 34, 33, 32, 42, 43, 44 with a minimum distance of 3 mm between each implant shoulder (Danza et al, 2011). The upper edges of the implants will be placed at the bone level and by achieving the necessary primary stability. After the implant placement any excessive bleeding will be stopped, by applying bone wax or cauterization. The bone level in relation to the implant margin will be scanned using CEREC Omnicam (Dentsply Sirona) and appropriate scan bodies will be used on all 6 implants to acquire a fixed reference for the later comparison on all 6 implants.

Additionally conventional impressions using Transfer Abutments and Aquasil (Dentsply DeTrey) will be performed for manufacturing of the dolder bars for immediate loaded implants on positions 33 and 43, and transgingival healing abutments will be applied to the implants on positions 32, 33, 42, 43. The Implants on positions 34 and 44 will be left for submerged healing using cover screws.

Finally, the mucoperiosteal flaps will be adapted and sutured tightly. For post-operative, radiological diagnostics a panoramic x-ray and single tooth x-rays of all implants will be taken. The administration of antibiotics, anti-inflammatory or other accompanying medication will be documented. Intraoperative Photographs will be taken.

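### The mixed model in section 11.2 takes the 4-month bone level as its response, without a baseline term, although the primary outcome and the planning means are changes in bone level

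*Protocol*

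**What the plan says.** Section 11.2 gives one model for the treatment comparison: "A linear mixed model will be applied to evaluate the influence of the treatment on the bone level after 4 months". On clustering it adds "Since there are 6 implants from one patient, the patients will be included as a random effect", and it makes treatment group a fixed effect. No insertion level is named. The sentence just before the model reads "The difference in bone loss over 4 months will be calculated for the three treatment groups"; it announces a calculation and does not make that quantity the model's response.

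The rest of the protocol is on the change scale:

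- Section 4 (Synopsis) gives the primary outcome as "periimplant bone level change in mm", and section 9.1 sets the main objective in the same terms.
- Section 5 describes the former study's measure as "assessment of marginal bone level related to the bone level at first stage surgery for loaded and non-loaded implants". Its mean reductions were 0.9 mm (loaded) and 0.33 mm (non-loaded).
- Section 11.2 plans on means of -0.910 and -0.330, a difference of -0.580, with SD 0.380.
- Section 10.1 says of the two scans: "The bone contours of the surface scan images will be superimposed to measure the differences in three-dimensional space".

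Two design statements bear on the consequence. Under Randomization and Blinding, "the positions of the immediately loaded and non-loaded submerged and transgingival healed implants are predetermined". Under Visit 2, "The upper edges of the implants will be placed at the bone level".

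**The concern.** A level at 4 months and a change over 4 months are different responses unless all implants start from the same level. The model as worded therefore tests something other than the stated endpoint and other than the quantity on which the trial was sized.

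In a randomised comparison, starting differences would average out. Here each healing protocol always occupies the same tooth positions (33/43 loaded, 32/42 transgingival, 34/44 submerged). Any mean difference in placement depth between those positions would be systematic and would be read as an effect of the healing protocol. A patient random effect cannot absorb it, because the difference lies within the patient and coincides exactly with treatment.

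The evaluation is described as exploratory, but section 11.2 sets a 5% significance level for all calculations and section 5 says the results are to lead to a subsequent trial. The reported contrast should have one clear meaning.

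**Working it through.** **1. The plan's own figures reproduce, on the change scale.** Inputs from section 11.2: difference 0.580, SD 0.380, two-sided 5%.

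- Two-group t-test, noncentral t: n = 7 per group gives 74.6% power and n = 8 gives 81.0%. The stated 8 is right.
- One-way ANOVA, three groups, variance of means 0.060, noncentrality n × 3 × 0.060 / 0.380²: n = 8 gives 75.2% and n = 9 gives 81.0%. The stated 9 is right.

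The means match the former study's changes (0.9 and 0.33 mm), so using change as the response needs no new sample size.

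**2. How an insertion offset enters.** For each implant, level at 4 months = level at insertion + change. For two protocols A and B:

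contrast of levels = contrast of changes + (mean insertion level at A's positions - mean insertion level at B's positions).

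An offset b therefore shifts the contrast by exactly b. With b = 0.10 mm the planned -0.58 becomes -0.48 or -0.68, depending on direction. With b = 0 nothing changes.

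**3. Size under assumed offsets.** The documents give no offset, so these are assumptions. With 20 patients and 2 implants per protocol there are 40 implants per protocol. The within-patient SD of the level is assumed to be 0.38 mm, borrowed from the planning SD.

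- SE of a pairwise contrast = 0.38 × √(2/40) = 0.085 mm.
- Residual df with patient and treatment in the model = 120 - 20 - 2 = 98.
- Rejection rate with equal true change: noncentral t, 98 df, noncentrality b / 0.085.

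| Assumed offset b (mm) | b / 0.58 | Rejection, 5% pairwise test |
|---|---|---|
| 0 | 0% | 5.0% |
| 0.05 | 8.6% | 9.0% |
| 0.10 | 17.2% | 21.4% |
| 0.20 | 34.5% | 64.5% |

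At b = 0.10 mm the rate is 37.5% if the SD is 0.27 mm and 15.2% if it is 0.48 mm.

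A separate simulation used the 2-df F test, with the offset on the loaded positions only and assumed SDs of 0.2 mm between patients and 0.2 mm for insertion level. The level model rejected in about 6%, 22%, 67% and 96% of null trials at offsets of 0, 0.1, 0.2 and 0.3 mm. The change model stayed at about 4% to 6%.

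**4. Secondary and conditional: the random effect.** Each patient has two implants per protocol. Let p be the share of within-patient variance that is patient-by-treatment (unknown, so assumed). The pooled mean square has expectation proportional to [38(1 + p) + 60(1 - p)]/98 = 1 - 22p/98, while the true variance of a pairwise contrast is proportional to 1 + p. So model SE / true SE = √[(1 - 22p/98)/(1 + p)].

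| p | Model SE / true SE | Type I error, F test | Type I error, pairwise |
|---|---|---|---|
| 0 | 1.00 | 4.9% | 5.0% |
| 0.1 | 0.94 | 6.9% | 6.4% |
| 0.3 | 0.85 | 11.5% | 9.6% |
| 0.5 | 0.77 | 16.8% | 13.2% |

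The error rates come from 200,000 simulated null datasets per row. Testing against the patient-by-treatment mean square (38 df) holds the error at about 5% throughout.

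**The case against.** The best reply is that change is plainly what is meant. The Synopsis, the objective, the scan method, the planning means and the sentence directly before the model all speak of change or loss, and the former study at the same department analysed change. One phrase departs from this. That is a fair reading of intent, but it does not remove the conflict: the only sentence that defines the tested response says something else.

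Second, implants are to be placed with their edges at bone level, using a surgical guide. The nominal starting level is then zero and the 4-month level is close to the change. Random placement error would add noise, not bias; only a mean offset tied to position would bias the contrast, and nothing in the document shows one. This stands, and it is why the bias may be zero. But flush placement is an intention. The former study placed implants the same way and still referred back to the first-stage level, and this protocol scans all six implants at insertion as a reference.

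Third, the offsets and variance shares are assumed, so the rejection rates illustrate a mechanism and do not measure a defect in this trial. That is correct.

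Fourth, a patient-by-treatment term is covariance detail that an analysis plan may settle. This is why it is offered only as a secondary improvement; the main point does not depend on it.

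**Conclusion.** The point holds. The model in section 11.2 names a response that differs from the primary outcome and from the scale of the sample size calculation, and it has no term for the insertion level. This is a conflict within the document, not a detail left for later.

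The size of the harm is unknown. It is zero if mean insertion levels are equal across positions, and otherwise equals the offset itself. Under the stated assumptions, an offset of 0.10 mm would be about a sixth of the planned effect and would raise a 5% pairwise test to roughly 21%. Loose wording is a plausible explanation, but the primary analysis should still be corrected, because the conflict concerns the main comparison and is easily removed. The sample size is unaffected.

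**What to change.** In section 11.2, name the per-implant change in scanned bone level from insertion to 4 months as the response of the mixed model. This is one phrase, and it uses the insertion and re-entry scans already planned.

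Adjusting for insertion level is optional. When positions differ at insertion, it is a different analysis from unadjusted change, so if used it should be labelled as such, for example as a sensitivity analysis.

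A cheap addition is a patient-by-treatment random effect, or averaging the two same-protocol implants within each patient before modelling change. Denominator df fall from 98 to 38. If the extra variance is zero, intervals widen by about 2% (ratio of the 97.5% t quantiles: 1.020).

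None of these steps separates healing protocol from tooth position. That confounding should remain a stated limitation.
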